- e. Respect the family's and school's schedule and demonstrate appreciation for their efforts to attend.
- f. Show consideration for the family's schedule by starting and ending on time.

3. Participation and Retention Benchmarks

Intervention Participation

Participants are expected to attend at least 70% or more of their prescribed FBT meetings, as indicated by their level of mastery of program knowledge and skills. The study staff will use a “case management approach” to ensure that each participant’s active involvement is cultivated and tracked, which will include opportunities for make-up sessions, telephone sessions, and home visits to maintain participation.

Families randomized into the UC group will attend medical appointments at the discretion of the physician according to their usual practices and availability, as well as the preferences of the participating family. As such, no benchmarks for usual care visits are specified.

Assessment Participation

Retention guidelines indicate that at least 80% of participants who are randomized will be retained at the 24-month assessment. It is estimated that drop-out rates will be higher in the first six months, as a steeper dropout rate was observed in the first four months of the recently completed, NIH funded COMPASS trial, than in the following 20 months. In order to maintain participation in assessment time points, we will offer flexible scheduling, make-up audio sessions, and home visits.

4. Participant Tracking

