observed SAEs and a given defined acceptable SAE rate. For example, suppose we define 2% as the maximum acceptable SAE rate. Then **Table 11** indicates that if the third SAE occurs in fewer than 41 intervention group subjects, then the guideline will have been exceeded because the SAE rate is greater than the acceptable 2% value with 95% certainty.

TABLE 11. MAXIMUM ACCEPTABLE SAE RATES

Number of Observed SAEs	Maximum Acceptable SAE Rate				
	2%	4%	6%	8%	10%
2	18	9	6	4	3
3	41	21	14	10	8
4	69	34	23	17	14
5	99	50	33	25	20

Several points about the above discussion are worth mentioning. First, we have used the term “guideline” instead of “rule” because we view the decision making process as one in which the guideline triggers a multifaceted discussion with the DSMB of whether the study should be stopped or modified because of the observed SAE rate. We do not view reaching the stopping boundary as a rule that should automatically lead to the termination of the study. Second, the rule will be applied both to parents and children separately. Third, we propose setting 2% as the maximum acceptable SAE rate because of the low anticipated SAE rate in this study.

At each DSMB meeting, recruitment and retention data will be presented to the DSMB. If recruitment is less than 90% of the target or if retention is less than 80% among randomized subjects, study investigators will present proposals for improvements in each of these two domains. Note that we use an 80% figure for retention because the original power computations had assumed a 20% dropout rate. Thus, an 80% retention rate is not an indication of reduced statistical power. If under performance by these definitions in either of these domains is present, the DCC will perform conditional power computations based on various scenarios regarding the degree of improvement that can be anticipated in recruitment and/or retention. As was the case in our original power computations, we will adopt the conservative approach of assuming that study dropouts provide no data. We propose that early termination be considered if the conditional power under the recruitment/retention scenarios the DSMB views as most realistic is less than 50%. Any final decision about recommending early termination will consider factors such as the impact of early stopping on information about secondary endpoints and covariate effects. It will also consider the adequacy of the measures that are proposed to increase recruitment and retention.

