Power computations for PLAN employ simulations and two-sided tests at the 0.05 level of significance. The simulations reflect the planned primary analysis of covariance and the fact that this is an individually randomized group treatment trial with the coach (N=3 per site) nested within the site (N=4 sites) in the FBT group but with no such nesting in the UC group. The analysis of covariance that is simulated in the power computations treats the 24-month value of the outcome measure as the dependent variable and the baseline value as a covariate. The use of this approach reflects the primary study goal of comparing 24-month values across groups, with the outcome being compared being percent over normalized BMI in the participating child. Each result is based on 1000 simulations.

Tabulated power values employ sample sizes of 528 and that are between 65% and 95% of that total. Effect size estimates are generated using considerations and preliminary data discussed below. Usual care data involving an intervention and subjects most similar to our UC group is provided by Kalarchian⁶¹ who randomized 81 8-12-year-old children with obesity to a usual care control condition and found an average percent overweight change of -0.17 ± 10.08 at 1 year. We expect some deterioration in this group at 2 years but will assume conservatively for the purpose of power computations that the two-year change will be 0 ± 10.08 in the UC group in the proposed research. Our estimated change in the FBT group begins with a review of seven studies^{20,62-67} authored by [name]. There were 314 overweight/obese children in those studies who received FBT interventions similar to the one we will employ. When we combined

the data for those 314 children, we found an overall average decrease in percent over BMI of 10.6 ± 15.3 at 24 months.

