In translating the above decrease of 10.6 ± 15.3 in percent over BMI at 24 months into the setting of the proposed research, we emphasize that the seven referenced studies implemented FBT in controlled academic settings where we anticipate better performance than is likely in the family practices we will employ in this study. To estimate the degree to which the effect is likely to be attenuated when we switch from highly controlled to more “real life” settings, we considered the following. The child weight management intervention MEND (Mind, Exercise, Nutrition, Do it) focused on children age 7-13 who exceeded the 91st weight percentile. MEND employed both (1) a community-based mass-implementation intervention⁶⁸ involving many programs and 9563 subjects who provided complete data and (2) a rigorous randomized trial⁶⁹ (N=116) analogous to the seven [name] studies referenced in the preceding paragraph. The 12-month results were reductions in BMI of 0.79 kg/m^2 in the community study as compared to 1.04 kg/m^2 in the intervention arm of the randomized trial. Thus, the reduction in the community-based MEND intervention was 76.0% of the magnitude that was observed in the family-based arm of the randomized trial.

Based on this 76.0%, our computations conservatively assume changes in the intervention group that are 50%, 60%, and 70% of the previously observed change of 10.6 ± 15.3 that was observed in the rigorous academic environment of [name] studies.^{20,62-67} Thus, we base our power on a comparison of projected reductions of 5.3 ± 15.3 (50% of 10.6 ± 15.3), 6.4 ± 15.3 (60% of 10.6), and 7.4 ± 15.3 (70% of 10.6) in the FBT group as compared to 0 ± 10.08 in the UC group. In addition, given projected standard deviations of 15.3 and 10.08 in the two groups, we use the maximum and the mean of those two values and thereby compute power assuming standard deviations of both 15.3 and 12.7. In performing the calculations summarized below, we emphasize that we will have actual or imputed 24-month data on all subjects. To see details of how we will impute the 24 month values when necessary, please see the section below titled “Implementation of the Intention-to-Treat Principle.”

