Table 1 contains the results of the power computations using the parameters discussed above, assuming the compound symmetry covariance structure in both study arms and assuming an intraclass correlation coefficient (ICC) in the UC group of 0.01 and ICCs in the FBT group of 0.04, 0.06, 0.10, and 0.15. We assume a small ICC in the UC group of 0.01 because there is no clustering within that group meaning that the ICC should be essentially zero. While we do not have data with which to estimate the ICC in the FBT group, we note that many cluster trials that involve group interventions have reported ICCs in the 0.01 to 0.05 range. Since the PLAN intervention is individualized and since we expect PLAN children to have no contact with one another, we do not face the impact on the ICC that is present in many cluster trials. This argues for a very small ICC in the FBT group. By contrast, the fact that the same coach will be responsible for multiple children will inevitably increase the ICC above where it might otherwise be. Based on these considerations, we tabulate power for ICCs in the FBT group that range from 0.04 to 0.15. However, the many other studies that have used group interventions while yielding ICCs below 0.05 suggests that the ICC ultimately observed in PLAN will be substantially less than 0.1.

Results in Table 1 indicate that if we recruit 100% of our original target of 528 families, power will be excellent for all tabulated scenarios with an ICC in the FBT group of 0.1 or less. For an ICC

no bigger than 0.1, power remains adequate for most scenarios if we recruit at least 80% of the target (N = 432). If recruitment is below the 80% figure, an adequate power of at least 0.8 requires either the smaller of the two tabulated standard deviations or a mean difference that is at least 60% of the value observed in [name] studies (difference at least 6.4).

Table 1: Statistical power for two sided tests at the 0.05 level of significance.

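### At N=528 one of the 18 power scenarios with FBT ICC up to 0.10 is 0.69, not excellent; 80% of target is 422, not 432; and the 20% dropout cited in the halting rules is not stated in the power section

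*Combined protocol and SAP*

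**What the plan says.** **Power section (Statistical Considerations, B.1, Sample Size and Statistical Power).** Power is simulated, with 1000 runs per cell, for FBT ICCs of 0.04 to 0.15, two SDs and three differences. On sample size the text says: "Tabulated power values employ sample sizes of 528 and that are between 65% and 95% of that total". The note to Table 1 defines N as randomized families. No dropout rate is given. Before presenting the results the section says: "we emphasize that we will have actual or imputed 24-month data on all subjects".

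It then summarises the table. At 528 families, "power will be excellent for all tabulated scenarios with an ICC in the FBT group of 0.1 or less". For ICC no larger than 0.1, "power remains adequate for most scenarios if we recruit at least 80% of the target (N = 432"). The next sentence uses 0.8 as the level for adequate power. The section also expects the observed ICC to be well under 0.1.

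**Study Halting Rules for Participant Safety.** The 80% retention limit is justified by the statement that "the original power computations had assumed a 20% dropout rate. Thus, an 80% retention rate is not an indication of reduced statistical power". Below the limit, "If under performance by these definitions in either of these domains is present, the DCC will perform conditional power computations". The convention for dropouts is: "As was the case in our original power computations, we will adopt the conservative approach of assuming that study dropouts provide no data".

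**Participation and Retention Benchmarks.** The guideline is that "at least 80% of participants who are randomized will be retained at the 24-month assessment".

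**The concern.** There are two separate problems.

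First, the summary of Table 1 makes a claim about every scenario up to ICC 0.10, and one cell of the table contradicts it. The summary also misstates the N for 80% of target. Someone who reads the text and not the table gets too favourable a picture.

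Second, the halting rules and the power section treat dropouts differently. One says that dropout was assumed at 20% and that dropouts contribute nothing. The other states no dropout and says that every child will have a measured or imputed outcome. The DSMB uses the first statement when it judges retention. If Table 1 contains no allowance, the assurance that 80% retention does not indicate lost power has no support in the plan's own power table. If Table 1 does contain one, the power section should say so.

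**Working it through.** **1. The 0.69 cell.** Inputs from the power section: two-sided alpha 0.05, 12 coaches (three at each of four sites) in the FBT arm only, FBT ICC 0.10, UC ICC 0.01, SD 15.3, difference 5.3. Allocation is 1:1 (Recruitment section), so n = 264 per arm and m = 264/12 = 22 families per coach. Two choices are mine: the UC ICC is applied to groups of the same size, and the test uses 11 df (12 coaches minus 1).

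- Design effects: FBT 1 + 21 x 0.10 = 3.10; UC 1 + 21 x 0.01 = 1.21.
- Variance of the difference: 15.3² x (3.10 + 1.21)/264 = 3.822; SE = 1.955.
- Noncentrality: 5.3/1.955 = 2.711; critical t on 11 df = 2.201.
- Power = 0.695, against 0.69 in the table. The cell is not a misprint.

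Its simulation error is √(0.69 x 0.31/1000) = 0.0146, so it lies (0.80 − 0.69)/0.0146 = 7.5 standard errors below 0.80.

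**2. The 80% figure.** 0.80 x 528 = 422.4, which matches the column heading in Table 1. 432/528 = 81.8%.

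**3. Tabulated power at N=528 and N=422, FBT ICC up to 0.10 (18 scenarios).**

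| ICC | SD | diff. 5.3 | diff. 6.4 | diff. 7.4 |
|---|---|---|---|---|
| 0.04 | 12.7 | 0.95 → 0.93 | 0.99 → 0.99 | 1.00 → 1.00 |
| 0.04 | 15.3 | 0.84 → 0.80 | 0.96 → 0.91 | 0.99 → 0.97 |
| 0.06 | 12.7 | 0.92 → 0.88 | 0.98 → 0.97 | 1.00 → 0.99 |
| 0.06 | 15.3 | 0.80 → 0.74 | 0.92 → 0.88 | 0.97 → 0.96 |
| 0.10 | 12.7 | 0.85 → 0.80 | 0.95 → 0.91 | 0.98 → 0.98 |
| 0.10 | 15.3 | 0.69 → 0.67 | 0.84 → 0.81 | 0.94 → 0.91 |

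At N=528 the range is 0.69 to 1.00, with one scenario below 0.80. At N=422 two are below 0.80. The losses run from 0 to 0.06 and sum to 0.47, so the mean is 0.47/18 = 0.026. If the simulations were independent, 10 of the 18 losses exceed simulation error (1.96 SE) and 8 do not.

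**4. Can the figures in Table 1 show whether dropout was built in?** The formula in step 1 can be rewritten as

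variance = SD² x (ICC_FBT + ICC_UC)/12 + SD² x [(1 − ICC_FBT) + (1 − ICC_UC)]/n.

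The first term does not involve n. The second is the individual-level part. I compared three versions with all 192 cells:

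- no dropout: root mean square error 0.016;
- 20% dropout and nothing else: 0.042;
- 20% dropout, with the baseline covariate removing 20% of the individual-level variance: 0.016.

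The first and third agree exactly, because n falls by a factor of 0.8 and so does the individual-level variance, and the two cancel. The 20% variance reduction is my assumption, since the plan gives no baseline correlation. But the plan does simulate an analysis of covariance, so some reduction of this kind is plausible. The numbers therefore cannot settle the question, and the second point rests on the text alone.

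**The case against.** The strongest reply concerns the retention statement. It refers to the original power computations, which may be a calculation that is not in these documents; Table 1 itself is marked as having had its Ns adjusted (9.29.19). If an earlier calculation assumed 20% dropout, the sentence is true of that calculation. A table indexed by randomized families is also where a dropout deduction could sit unseen. This stands. A reader might infer that Table 1 has no dropout allowance, that the halting-rules statement is therefore false, and that 80% retention simply is the N=422 column. The documents do not support that: no sentence says that dropout was left out, the tabulated values fit either way (step 4), and if an allowance is already included, moving to N=422 counts dropout twice.

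It can also be said that the effect is small. The section expects an ICC well below 0.1, it already calls power at 80% of target adequate only for most scenarios, the full table is printed beside the text, and conditional power, once triggered, counts dropouts as giving no data. All of this is fair and limits the weight of the point. It does not rescue the summary sentence, which expressly covers ICCs up to 0.1 and admits no exception.

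**Conclusion.** Two statements in the power section are wrong as written. Power at N=528 is not excellent in all 18 scenarios with FBT ICC up to 0.10: it ranges from 0.69 to 1.00, with one scenario below the section's own 0.8. And 80% of 528 is 422.

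The third item is an unreconciled conflict in current text, not a proven error. The halting rules rely on a 20% dropout assumption with no data from dropouts; the power section states no such assumption and counts an outcome for every child. The size depends on a fact that the documents do not give. If Table 1 already allows for 20% dropout, 80% retention costs nothing relative to it. If it does not, the worst case is the N=422 column: a loss of 0 to 0.06 (mean 0.026) for ICC up to 0.10, and two scenarios below 0.80 instead of one.

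That is a bound, because clinic measurements and multiple imputation may recover part of the loss. The plan gives no recovery rate. Assuming no built-in allowance, and that all, half or none of the information from the 106 lost families is recovered (effective N 528, 475, 422), the step 1 formula at difference 5.3 and SD 15.3 gives 0.834, 0.809, 0.777 at ICC 0.04; 0.785, 0.761, 0.732 at ICC 0.06; and 0.695, 0.674, 0.650 at ICC 0.10.

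The practical effect is minor.

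**What to change.** **Power section.** Replace the summary for N=528 with: power for FBT ICC up to 0.10 ranges from 0.69 to 1.00, and one of 18 scenarios (ICC 0.10, SD 15.3, difference 5.3) is below 0.80. Change 432 to 422.

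**Power section and halting rules together.** State whether the power in Table 1 includes a 20% dropout allowance, and reconcile this with the statement that all subjects will have actual or imputed outcomes.

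- If it does, say so in the power section and keep the halting-rules sentence.
- If it does not, remove the claim that 80% retention is no indication of reduced power. Say instead that full recruitment with 80% retention corresponds at worst, with no data from dropouts, to the N=422 column, and give the loss: 0 to 0.06, mean 0.026, with scenarios below 0.80 going from one to two for ICC up to 0.10.

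**Cost.** Wording, plus a look at the simulation program to see what was assumed. No extra families are needed, and neither the 80% benchmark nor any analysis changes.
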